3.0 Introduction

This statistical analysis plan (SAP) describes the statistical analysis to be completed by the AbbVie Clinical Statistics Department for study Protocol 1311.30 dated 10 December 2015.

This SAP will provide details to further elaborate statistical methods as outlined in the Protocol 1311.30 and will describe analysis conventions to guide the statistical programming work. The SAP will be signed off before the study database is locked.

Analyses will be performed using SAS[®] version 9.4 (SAS Institute, Inc., Cary, NC 27513) or higher using the UNIX operating system.

4.0 Study Objectives, Design and Procedures

4.1 Primary Study Objective

The main objectives of this study are to assess the efficacy and safety of risankizumab compared to adalimumab in subjects with moderate to severe chronic plaque psoriasis. The primary efficacy evaluation will be performed at Week 16. The study will also evaluate the efficacy of a 28-week treatment with risankizumab in subjects who were initially treated with adalimumab for 16 weeks, achieving insufficient or only partial response with adalimumab, and then switched to risankizumab treatment from Week 16 to Week 44.

In addition, this trial will assess pharmacokinetics (PK) and the emergence of anti-drug antibodies (ADA) and their effect on efficacy and safety. Moreover, it will be explored how the use of risankizumab may influence gene and protein expression levels and disease specific protein markers. PK and ADA analyses, exploratory biomarker analyses, and metabolic risk factor analyses, will not be included in this SAP.

4.2 Design Diagram

This confirmatory multi-national, randomized, double-blind, double dummy, active controlled, parallel design study compares risankizumab with adalimumab. In total, approximately 600 subjects with moderate to severe chronic plaque psoriasis will be randomized in this trial.

Subjects are included in the study once they have signed the informed consent. Subjects suitable after screening will be eligible to participate in the 44 week treatment period shown in [Figure 1](#).

Subjects will be blinded to treatment. Subjects in each dose group will receive the same injections at each designated time point, in order to maintain blinding.

Part A:

Part A is a 16-week, double-blinded, active-controlled treatment period during which subjects will be randomized at a 1:1 ratio to risankizumab or adalimumab. The randomization will be stratified by weight (≤ 100 kg vs. > 100 kg) and prior exposure to TNF antagonists (0 vs. ≥ 1). Subjects randomized to risankizumab will receive 2 syringes of risankizumab active drug (2×75 mg) at randomization and at Week 4, and adalimumab placebo at randomization (2 syringes) and 1 adalimumab placebo syringe at Weeks 1, 3, 5, 7, 9, etc. up to Week 15. Subjects randomized to adalimumab will receive 2 syringes adalimumab at randomization (2×40 mg) followed by 1 syringe adalimumab (40 mg) at Weeks 1, 3, 5, 7, 9, 11, 13 and 15. These subjects will also receive 2 syringes of risankizumab placebo at randomization and at Week 4.

Part B:

[figure not shown]
At Week 16, subjects initially on risankizumab will stay on risankizumab. These subjects will receive 2 syringes of risankizumab (2×75 mg) at Week 16 and 28, and 2 syringes of risankizumab placebo at Week 20 and 32. They will also receive 1 syringe of adalimumab placebo at Weeks 17, 19, 21, 23, etc. up to Week 41.

At Week 16, subjects initially on adalimumab and have $<$ PASI 50 response ($<$ 50% reduction in Psoriasis Area and Severity Index (PASI)) will be switched to risankizumab. These subjects will receive 2 syringes of risankizumab (2×75 mg) at Week 16, 20, and 32, and 2 syringes of risankizumab placebo at Week 28. They will also receive 1 syringe of adalimumab placebo at Weeks 17, 19, 21, 23, etc. up to Week 41.

At Week 16, subjects initially on adalimumab and \geq PASI 90 will be stay on adalimumab. These subjects will receive 2 syringes of risankizumab placebo at Week 16, 20, 28 and 32. They will also receive 1 syringe of adalimumab at Weeks 17, 19, 21, 23, etc. up to Week 41.

At Week 16, subjects initially on adalimumab and \geq PASI 50 and $<$ PASI 90 will be re-randomized at a 1:1 ratio to risankizumab or adalimumab. Subjects re-randomized to risankizumab will receive 2 syringes of risankizumab (2×75 mg) at Week 16, 20 and 32, and 2 syringes of risankizumab placebo at Week 28. They will also receive 1 syringe of adalimumab placebo at Weeks 17, 19, 21, 23, etc. up to Week 41. Subjects re-randomized to adalimumab will receive 2 syringes of risankizumab placebo at Week 16, 20, 28 and 32. They will also receive 1 syringe of adalimumab at Weeks 17, 19, 21, 23, etc. up to Week 41.

Figure 1. Trial Design

BI 655066 is risankizumab.

4.3 Sample Size

This study is designed to show a benefit of risankizumab over adalimumab in terms of PASI 90 response and static Physician Global Assessment (sPGA) of clear or almost clear (sPGA of 0 or 1) at Week 16. This study is also powered to show a benefit in PASI 90 response at Week 44 between the subjects re-randomized to continue on adalimumab vs. subjects randomized to risankizumab at Week 16.

Based on the assumption that the Week 44 PASI 90 rate will be approximate 40% for adalimumab and 70% for risankizumab for the subjects who are re-randomized at Week 16, a total of 120 subjects will result in > 90% power for the primary efficacy analysis in Part B using a type-I error rate at 5%. See Table 1 sample size calculations for different scenarios. Assuming for those subjects originally randomized to adalimumab the response rate at Week 16 for PASI 90 and PASI 50 are 45% and 85%, respectively, then this leaves approximately 40% of subjects expected to fall in the more than or equal

to PASI 50 and less than PASI 90 range and thus be eligible for re-randomization. This requires that 300 (40% of 300 = 120) subjects be randomized to adalimumab at randomization.

Based on the outcome from Trials 1311.1 and 1311.2, the PASI 90 response rate at Week 16 is assumed to be at least 65% in the risankizumab arm. For the primary analysis comparing risankizumab to adalimumab, sample sizes of 300 per arm will allow for > 90% power assuming 70% and 50% PASI 90 response rates for risankizumab and adalimumab, respectively. See [Table 2](#) for more sample size calculations.

Table 1. Sample Sizes for 90% Power for Testing Against Adalimumab Using PASI 90 at Re-Randomization

Risankizumab	Adalimumab	Delta	Re-Randomization Ratio Risankizumab:Adalimumab = Total N
65%	40%	25%	82:82 = 164
70%	45%	25%	80:80 = 160
70%	40%	30%	56:56 = 112
75%	45%	30%	54:54 = 108
80%	50%	30%	51:51 = 102

Table 2. Sample Sizes for 90% Power for Testing Against Adalimumab Using PASI 90

Risankizumab	Adalimumab	Delta	Randomization Ratio Risankizumab:Adalimumab = Total N
65%	50%	15%	226:226 = 452
70%	55%	15%	217:217 = 434
70%	50%	20%	124:124 = 248
75%	55%	20%	118:118 = 236
70%	45%	25%	80:80 = 160
75%	50%	25%	77:77 = 154

Based on the outcome from Trials 1311.1 and 1311.2, the achievement of sPGA clear or almost clear rate at Week 16 is assumed to be at least 85% in the risankizumab arm.

Assuming 70% rate for the adalimumab arm, by using the PASI 90 required sample sizes, 300 subjects per treatment arm will provide at least 90% power for sPGA endpoint. See [Table 3](#) for more sample size calculation.

As PASI 90 and sPGA are highly correlated, this trial will have > 90% power for comparing risankizumab arm to adalimumab arm on both of these endpoints.

Table 3. Sample Sizes for 90% Power for Testing Against Adalimumab Using sPGA Clear or Almost Clear

Risankizumab	Adalimumab	Delta	Randomization Ratio Risankizumab:Adalimumab = Total N
85%	72.5%	12.5%	223:223 = 446
85%	70%	15%	161:161 = 322
87.5%	72.5%	15%	148:148 = 296
87.5%	70%	17.5%	113:113 = 226

Calculations were performed using ADDPLAN Version 6.0.4.

4.4 Interim Analysis

Unblinded data will be reviewed during the study by an independent data monitoring committee (DMC). The membership, roles and responsibilities and activities of the DMC will be defined in a written charter. The DMC will include representatives from external safety experts who do not directly involve in the study. Clinical site personnel and the study team will remain blinded to the randomized treatment assignments during the course of the study. Communications from the DMC to the study team will not contain information that could potentially unblind the study personnel. Since there is no efficacy analyses for early stopping, no alpha adjustment is needed.

No other interim analyses are planned.

5.0 Analysis Populations

5.1 Definition for Analysis Populations

Efficacy Population:

Intent to Treat (ITT) Populations: The ITT Population in each period will be used for efficacy analyses.

- The ITT Population in Part A (ITT_A) is defined as all subjects who are randomized at Baseline.
- The ITT Population in Part B who are re-randomized (ITT_B_RR) is defined as all subjects who start with adalimumab at Baseline and are re-randomized at Week 16.
- The ITT Population for PASI 90 responders at the entry of Part B (ITT_B_R) is defined as all subjects who start with adalimumab at Baseline and achieve PASI 90 at Week 16 and receive at least one dose of active adalimumab on or after Week 16.
- The ITT Population for PASI 50 non-responders at the entry of Part B (ITT_B_NR) is defined as all subjects who start with adalimumab at Baseline and fail to achieve PASI 50 at Week 16 and receive at least one dose of active risankizumab on or after Week 16.
- The ITT Population in Part B continuously receiving risankizumab (ITT_B_RZB) is defined as all subjects who start with risankizumab at Baseline and receive at least one dose of active risankizumab on or after Week 16.

The ITT Population will be analyzed by the treatment group as randomized and as re-randomized where applicable.

Per-Protocol (PP) Population: To evaluate the impact of protocol deviations on the primary and ranked secondary endpoints, additional analyses will be performed on the Per-protocol Populations. The Per-protocol Population will include those who were most compliant with the protocol in ways that could impact the primary and ranked secondary

endpoints. Final results and the criteria for exclusion of subjects will be determined via classification prior to database lock for data pertaining to the DB period. The PP population at Part A (PP_A) is defined as all ITT_A subjects meeting all the following criteria:

- Subjects must receive at least 75% of planned risankizumab injections, as well as at least 75% of planned adalimumab injections, including dummy placebo injections, per randomized, in Part A.
- Subjects must have either a PASI or sPGA assessment post-baseline in Part A.
- Inclusion Criterion 4: Subjects must have stable moderate to severe chronic plaque psoriasis baseline:
 - Have an BSA $\geq 10\%$ and
 - Have a PASI ≥ 12 and
 - Have an sPGA ≥ 3 .

Primary and ranked secondary efficacy endpoints at Week 16 will be analyzed on the PP_A Population.

The PP Population at Part B for re-randomized subjects (PP_B_RR) is defined as all subjects from the ITT_B_RR Population who meet all the following criteria:

- Subjects must receive at least 75% of planned risankizumab injections, as well as at least 75% of planned adalimumab injections, including dummy placebo injections, per re-randomized, in Part B.
- Subjects must have at least one PASI assessment post re-randomization in Part B.
- Subjects must have a response of PASI 50 – < 90 at re-randomization.

The primary and ranked secondary efficacy endpoint at Part B at Week 44 will be analyzed on the PP_B_RR Population.

PP Populations will be analyzed by the treatment group as randomized (or re-randomized).

Safety Populations (Safety):

The Safety Populations will be used for safety analyses in different study parts.

Each ITT Population will have a corresponding safety population (Safety) defined which require subjects to have at least one dose of active study drug during the analysis period.

Complete safety tables will be provided for the Safety_A Population and the Safety_B_RR population. AE overview tables will be provided for other safety populations.

The Safety Population will be analyzed based on the actual treatment received at the randomization visit (Safety_A) and at the re-randomization visit (Safety_B_RR).

In addition, an All Risankizumab Treated Population (ALL_RZB) is defined as all subjects who receive at least one dose of risankizumab 150 mg in the study. The ALL_RZB Population will be used for safety analyses. Complete safety tables will be provided in the ALL_RZB Population.

Notations for Treatment Groups:

Part A:

- ADA: Subjects randomized to adalimumab
- RZB: Subjects randomized to risankizumab 150 mg

Part B:

- RZB/RZB: Subjects randomized to risankizumab and continue with risankizumab
- ADA/ADA: Subjects randomized to adalimumab and stay with adalimumab at Week 16
- ADA/RZB: Subjects randomized to adalimumab and switched to risankizumab at Week 16

ALL_RZB:

- RZB: Subjects who received at least one dose of risankizumab 150 mg

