2.2 TRIAL OBJECTIVES

The main objectives of this study are to assess the efficacy and safety of BI 655066 compared to adalimumab in patients with moderate to severe chronic plaque psoriasis. The primary efficacy evaluation will be performed at 16 weeks and an assessment of maintenance of response will be performed at 44 weeks. The study will also evaluate the efficacy of a 28 week treatment with BI 655066 in patients who were initially treated with adalimumab for 16 weeks, achieving insufficient or only partial response with adalimumab, and then switched to BI 655066 treatment from Week 16 to Week 44.

In addition, this trial will assess PK and the emergence of anti-drug antibodies (ADA) and their effect on efficacy and safety. Moreover, it will be explored how the use of BI 655066 may influence gene and protein expression levels and disease specific protein markers.

Lastly, the influence of study treatment on some metabolic risk factors will be looked into.

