6.2.3.1 Early treatment and trial termination

If study medication is discontinued prior to the planned [Flow Chart](#) visit EOT, every effort should be made to have the patient continue in the trial and complete all of the remaining trial visits and procedures including EOT and EOO Visit; with the EOO Visit to be performed 4 weeks after the EOT Visit.

If a patient cannot or will not continue in the trial, the patient should complete EOT Visit procedures instead of the next planned treatment period visit. These patients should be registered as prematurely discontinued in IRT and return to the clinic for End of Observation Visit 16 (± 1) weeks after their last administered dose of BI 655066 (active or placebo). Patients who discontinue from the trial prematurely will not have the option to participate in the open label extension (OLE) study.

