7.3 PLANNED ANALYSES

The efficacy analyses will be based on the intent-to-treat principle, comprising all participants who were randomised and received at least one dose during the trial. Misrandomized patients are by definition screening failures and therefore are not included in the intended to treat population. Efficacy analyses will be based on the planned treatment (i.e., the treatment assigned at randomization); this set of patients is called the Full Analysis Set (FAS). Safety analyses will be based on the actual treatment received at the Randomization Visit; this set of patients is called the Safety Set (SAF).

Important violations of the protocol will include key inclusion and exclusion violations, incorrect medications taken, compliance with study medication, incorrectly re-randomized or not re-randomized, concomitant use of restricted medications, and any other violations of the protocol deemed important by the study team. All decisions concerning important protocol violations will be made prior to unblinding of the database. A per-protocol set (PPS) will be defined excluding patients with violations that affect Week 16 efficacy. A secondary re-randomized per-protocol set (RRS-PPS) will be defined excluding those patients with violations affecting the patients included in the Week 44 assessment of re-randomization. The hypothesis tests as described in [Section 7.2](#) will be repeated on the PPS or RRS-PPS populations, as appropriate.

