10.0 Efficacy Analysis

10.1 General Considerations

The treatment effect will be evaluated based on a two-sided significance level of 0.05 (when rounded to three decimal places).

Efficacy variables will be summarized in all ITT populations. The efficacy analysis will be conducted in the ITT_A and the ITT_B_RR populations. Only the primary and ranked secondary variables will be analyzed for the per-protocol populations using primary approach to handle missing data as described below.

Subjects' actual weight category and prior TNF antagonist exposure will be used as the strata in the stratified analyses.

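### The set ITT_B_RZB is labelled ITT but requires a dose on or after Week 16, so the descriptive Week 20–44 rates for the risankizumab arm leave out patients lost in Part A

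*SAP*

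**What the plan says.** SAP 5.1 lists five ITT populations. The entry for the original risankizumab arm begins "The ITT Population in Part B continuously receiving risankizumab (ITT_B_RZB" and defines its members as "all subjects who start with risankizumab at Baseline and receive at least one dose of active risankizumab on or after Week 16". Two of the other sets carry no dosing condition: "The ITT Population in Part A (ITT_A) is defined as all subjects who are randomized at Baseline", and ITT_B_RR is "all subjects who start with adalimumab at Baseline and are re-randomized at Week 16".

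SAP 10.1 states: "Efficacy variables will be summarized in all ITT populations". It confines the efficacy analysis proper to ITT_A and ITT_B_RR. SAP Table 4 gives ITT_A its PASI and sPGA windows, the last being Week 16 (to Day 127). SAP Table 8 gives the Week 20–44 windows to the Part B sets only.

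The protocol uses a wider set. Section 7.3 bases efficacy on a population "comprising all participants who were randomised and received at least one dose during the trial", with no Week 16 condition. Section 7.5 counts a binary endpoint as failed when no later data exist. Section 2.2 promises that "an assessment of maintenance of response will be performed at 44 weeks". Section 6.2.3.1 says that when drug is stopped early, "every effort should be made to have the patient continue in the trial and complete all of the remaining trial visits". SAP 14.1 records that the populations were defined in detail, but does not say that this one is narrower than the protocol's.

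**The concern.** Patients who start on risankizumab are never re-randomised, so their Week 44 result can be reported on everyone randomised. The SAP restarts the denominator at Week 16 instead, and selects on something that happens after randomisation: still being on drug. Non-responder imputation works only inside a set, so it cannot reach a patient who has been removed from the set.

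Two kinds of patient are lost. The first left the trial in Part A. SAP 10.1.4 would count those who left for worsening disease as non-responders at all later visits, but here they have no later visits in any table. The second stopped drug in Part A and kept attending, as the protocol asks; their Week 20–44 scores enter no efficacy set.

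At stake is the description of maintenance of response in the risankizumab arm. The Week 16 rate and the Week 20–44 rates rest on different denominators, so a curve drawn through them changes population at Week 16. A reader who takes the ITT label at face value will not expect that.

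**Working it through.** **1. The plan's own figures.** The documents state no expected Week 44 rate for the original risankizumab arm and no dropout rate. Their only sizing figures are in SAP 4.3. For PASI 90 at 70% versus 50%, two-sided 5% and 90% power:

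n = [1.960·√(2·0.6·0.4) + 1.2816·√(0.7·0.3 + 0.5·0.5)]² / 0.20² = (1.358 + 0.869)² / 0.04 = 124 per arm,

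which matches SAP Table 2. All 15 rows of SAP Tables 1–3 reproduce within one patient per arm, and 300 per arm gives 99.9% power at 70% versus 50%. None of this involves ITT_B_RZB.

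**2. Which set covers which weeks (SAP 5.1, Tables 4 and 8).**

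| Set | Dosing condition on or after Week 16 | PASI/sPGA visits |
|---|---|---|
| ITT_A (both arms) | none | Weeks 4–16 |
| ITT_B_RR (adalimumab, re-randomised) | none | Weeks 20–44 |
| ITT_B_R (adalimumab, PASI 90 at Week 16) | active adalimumab | Weeks 20–44 |
| ITT_B_NR (adalimumab, below PASI 50) | active risankizumab | Weeks 20–44 |
| ITT_B_RZB (risankizumab throughout) | active risankizumab | Weeks 20–44 |

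Only the last row holds the original risankizumab arm after Week 16.

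**3. Size.** Let p be the rate among all randomised, d the share with no Part B dose, and q the response rate among those excluded. The set then shows

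r = (p − d·q) / (1 − d).

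If every excluded patient is a non-responder (q = 0), r = p/(1 − d). Since q cannot be below zero, this is the upper bound.

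Take N = 300 (SAP 4.3). The values p = 75% (225 responders) and d are assumptions:

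| d | Excluded | Upper bound, q = 0 | q = 50% |
|---|---|---|---|
| 2% | 6 | 225/294 = 76.5% | (75 − 1.0)/98 = 75.5% |
| 5% | 15 | 225/285 = 78.9% | (75 − 2.5)/95 = 76.3% |
| 8% | 24 | 225/276 = 81.5% | (75 − 4.0)/92 = 77.2% |

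At q = 75% the gap is zero, and above that the set would understate the rate. The upper bounds for other values of p are 71.4%, 73.7% and 76.1% at p = 70%, and 86.7%, 89.5% and 92.4% at p = 85%, for the same three values of d.

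**The case against.** The best defence is that little rests on this set. The Week 44 PASI 90 endpoint is restricted to re-randomised patients (protocol 5.1.2 and 7.3.2), SAP 10.3.2 analyses the Week 44 sPGA endpoints in ITT_B_RR, and ITT_B_RZB has no comparator and no test. That stands. A reader might infer that the trial's tested Week 44 results are biased; the documents do not support this.

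Second, a reader might take 1/(1−d) as the actual inflation. It is only a ceiling. Patients who stop drug but attend are scored as observed, and some may respond. Protocol 1.2 reports that 24 weeks after a single dose 71% of patients still had PASI 75 and 48% had PASI 90. This also stands. Overstatement is certain only for patients who leave the trial.

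Third, the definition is disclosed, and SAP 8.0 plans disposition tables for ITT_A by arm and for ITT_B_RZB, so a reader could rebuild a rate with everyone in the denominator. This is partly right. Such a rate would count all excluded patients as failures and could not recover the observed scores of those who kept attending. Describing patients who entered Part B is a legitimate summary, but not under an ITT label and not as the only one.

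Fourth, one might want to strip the dosing condition from ITT_B_R and ITT_B_NR as well. For ITT_B_NR this would misclassify patients. Under protocol 4.1.4, patients whose Week 16 visit falls after Day 126 continue their previous treatment whatever their PASI. An adalimumab patient below PASI 50 could then enter the switched-to-risankizumab group while still on adalimumab. This objection stands in full.

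**Conclusion.** The point holds for the descriptive Week 20–44 results of the original risankizumab arm. The set is called ITT, selects on dosing after Week 16, and is the only one that carries the arm forward. That departs from the protocol's efficacy set (7.3) and its failure rule (7.5), and leaves the Week 44 maintenance objective without an all-randomised summary.

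The co-primary, ranked and Part B tests, the type I error and the power are unaffected. At an assumed 75% rate, the inflation is at most 1.5, 3.9 and 6.5 percentage points for d of 2%, 5% and 8%, and smaller if some excluded patients are observed responders. Both the rate and d are assumptions, so the documents cannot narrow this further. This is a cheap improvement to reporting and does not threaten the trial's confirmatory conclusions.

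**What to change.** - Add to the SAP a Week 20–44 summary of PASI and sPGA response, with non-responder imputation, for all patients randomised to risankizumab (the ITT_A risankizumab arm, about 300).
- Count its visit windows from the first Part A dose, or from randomisation if never dosed. Table 8 cannot be reused as it stands: it counts from the first Part B dose, and its fallback for undosed patients covers only those re-randomised. SAP 6.0 already counts days from the first Part A dose for analyses across both parts. SAP Table 14 (vital signs, counted from the first risankizumab dose) has Week 20–44 windows that could serve as a template, from Days 128–155 for Week 20 to Days 296–323 for Week 44.
- Rename ITT_B_RZB, for example *treated in Part B*, and keep it as a supplementary summary.
- Leave ITT_B_R and ITT_B_NR unchanged.

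The cost is one new window table, one more row per visit, and a Week 44 rate that may be slightly less favourable. No new data, patients or alpha are needed.
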